1.0 TRIAL SUMMARY

Abbreviated Title	Combination Pembrolizumab and Olaparib in the Treatment of Patients with Advanced Cholangiocarcinoma
Trial Phase	II
Clinical Indication	Advanced cholangiocarcinoma who have failed or cannot tolerate 1 st line systemic therapy
Trial Type	Single arm, single-site
Type of control	None
Route of administration	Oral and intravenous
Trial Blinding	None
Treatment Groups	Olaparib plus pembrolizumab
Number of trial participants	36
Estimated enrollment period	24
Estimated duration of trial	36
Duration of Participation	12
Estimated average length of treatment per patient	12

2.0 TRIAL DESIGN

2.1 Trial Design

We propose an open label, one-arm study to assess the safety and efficacy of olaparib and pembrolizumab in patients with cholangiocarcinoma who have progressed on or cannot tolerate gemcitabine-based therapy.

The primary objective of the study is to assess the ORR of patients with advanced cholangiocarcinoma receiving a combination of pembrolizumab and olaparib. It is hypothesized that the addition of olaparib will improve the response rate of second line systemic therapy from 17.5% to 35% in patients with advanced cholangiocarcinoma.

The study is designed to enroll 33 subjects (for 85% power) with advanced stage cholangiocarcinoma to test the hypothesis that the combination of olaparib and pembrolizumab will increase the ORR in comparison with the ORR from second line systemic chemotherapy (historical control) in this patient population. As our primary study endpoint, which is also being used to determine the sample size of the study, we propose that the combination of olaparib and pembrolizumab will increase the ORR to 35% from 17.5% (achieved with systemic cytotoxic chemotherapy including mFOLFOX—historical control). To allow a 10% patient drop off rate, we expect to enroll a total of 36 subjects into this study. In addition, as secondary study endpoints we expect to see an increase in the PFS and OS of patients receiving combination therapy compared to cytotoxic chemotherapy.

[figure not shown]
A Phase II, Single-arm Study of Combination Pembrolizumab and Olaparib in the Treatment of Patients with Advanced Cholangiocarcinoma
Version 2.1: 17Mar2023

In this study, we propose the collection of three biopsies—one at baseline prior to the start of treatment, one at the beginning of week 4, three weeks after the administration of combination olaparib and pembrolizumab, and one at the time of cancer progression—for the elucidation of exploratory study endpoints. Patients will have a CT or MRI scan at the beginning of treatment and then every 6 weeks thereafter for the first six months of study treatment administration, then every 9 weeks for up to 12 months after the start of treatment, followed by every 12 weeks up to 24 months on study. All patients will continue to receive olaparib and pembrolizumab combination treatment as tolerated unless unacceptable toxicities or cancer progression occur, at which time therapy will cease. In the absence of any problems, the planned study duration is 20-36 months.

2.2 Trial Diagram

Medications:

1. Olaparib at 300mg twice per day, will be administered orally starting on study day 1.
2. Pembrolizumab will be administered intravenously at 200mg every 3 weeks starting on study day 1.

3.0 OBJECTIVE(S) & HYPOTHESIS(ES)

3.1 Primary Objective(s) & Hypothesis(es)

(1) Objective:

Assess the objective response rate (ORR) of patients receiving pembrolizumab and olaparib combination therapy.

(2) Hypothesis:

The combination of olaparib and pembrolizumab regimen will improve the response rate of second line systemic therapy from 17.5% to 35% in patients with advanced cholangiocarcinoma, based on RECIST1.1.

A Phase II, Single-arm Study of Combination Pembrolizumab and Olaparib in the Treatment of Patients with Advanced Cholangiocarcinoma
Version 2.1: 17Mar2023

3.2 Secondary Objective(s) & Hypothesis(es)

(1) Objective:

1. Assess the duration of response (DOR) of patient receiving pembrolizumab and olaparib, taking best overall response to progression.
2. Assess progression free survival (PFS) of patients receiving pembrolizumab and olaparib taking best overall response to progression or death from any cause, whichever occurs first.
3. Assess overall survival (OS) of patients receiving pembrolizumab and olaparib from baseline to date of death or last follow up.
4. Assess the safety and tolerability of combined pembrolizumab and olaparib therapy.

(2) Hypothesis:

We propose that a PFS of 24 weeks and an OS of 40 weeks is clinically meaningful in patients who receive the combination of pembrolizumab and olaparib following failure on frontline therapy (due to cancer progression or intolerance of treatment).

3.3 Exploratory Objective

(1) Objective:

1. To correlate in tumor samples the baseline density of CD3 and CD8 in the tumor interior and invasive margin, the expression of PD-L1, and the clonality of the T-cell repertoire with ORR, DOR, PFS, and OS.
2. To assess in tumor samples the baseline density of CD3 and CD8 in the tumor interior and invasive margin, the expression of PD-L1, and the clonality of the T-cell repertoire at baseline and after three weeks of treatment, and then correlate these assessments with ORR, DOR, PFS, and OS.
3. To compare in tumor samples the density of CD3 and CD8 in the tumor interior and invasive margin, the expression of PD-L1, and the clonality of the T-cell repertoire at three time points: at the time of disease progression, after three weeks of treatment, and at baseline.
4. To correlate in the cholangiocarcinoma tissue the baseline expression of ERCC (DRCC+/-) or the baseline mutation status of IDH1 or 2 (mutant or non-mutant) with ORR, DOR, PFS, and OS.

(2) Hypothesis:

A Phase II, Single-arm Study of Combination Pembrolizumab and Olaparib in the Treatment of Patients with Advanced Cholangiocarcinoma

Version 2.1: 17Mar2023

Given the low expression of the ERCC1 protein in the majority of cholangiocarcinomas, together with relative frequent IDH1/2 mutations found in these tumor types, we hypothesize that the combination of PARP inhibition and immune checkpoint blockade will produce a durable anti-tumor response against cholangiocarcinoma by synergistically inducing DNA damage, increasing tumor antigen number and producing durable immune response against cholangiocarcinoma. Therapies that target the programmed death-1 (PD-1) receptor have shown unprecedented rates of durable clinical responses in a sub-group of patients with various cancer types [1-5]. Biomarkers in patient tumor that will predict response to anti-PD-1 therapy are being actively investigated. One mechanism by which cancer tissues limit the host immune response is via upregulation of PD-1 ligand (PD-L1) and its ligation to PD-1 on antigen-specific CD8+ T cells [6, 7]. Recent research has reported that tumor regression after therapeutic PD-1 blockade requires pre-existing CD8+ T cells that are negatively regulated by PD-1/PD-L1-mediated adaptive immune resistance [8].

We propose that olaparib will increase the response of pembrolizumab by inducing DNA damage, increasing tumor antigen number, and producing durable immune response against cholangiocarcinoma. We expect that cancer cells with low expression of the ERCC1 proteins or with IDH1/2 mutations will have more DNA damage upon olaparib treatment than cancer cells that have normal expression of the ERCC1 protein, or are without IDH1/2 mutations.

In this study, we will first test whether the effect of olaparib and pembrolizumab treatment on tumor infiltrating lymphocytes, the level of PD-1 and PD-L1 expression, and clonality of the T-cell repertoire differs between low ERCC1/IDH1/2 mutant and normal ERCC1/non IDH1/2 mutant tumor cells. Then we will examine whether the change of tumor infiltrating lymphocytes and the level of PD-1 and PD-L1 expression correlates with clinical response in patients treated with pembrolizumab and olaparib combination therapy.

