8.2.3 Analysis Plans for Exploratory Objectives

The biomarkers which are of interest are programmed death ligand-1 (PD-L1) levels, immune score as determined by the density of CD3 and CD8 in the tumor interior and invasive margin(s) of the tumor, the clonality of the T-cell repertoire in the tumors, the expression of ERCC, and the mutation status of IDH1 or 2 in the same cholangiocarcinoma tissue. We will assess the biomarker levels at baseline, after four weeks of combination olaparib and pembrolizumab therapy, and at the time of cancer progression. The expression of ERCC and the mutation status of IDH1 or 2 in

A Phase II, Single-arm Study of Combination Pembrolizumab and Olaparib in the Treatment of Patients with Advanced Cholangiocarcinoma

Version 2.1: 17Mar2023

the same cholangiocarcinoma tissue will only be assessed at baseline. For different levels of biomarkers at baseline or change between different time points, we are interested in correlating them with patients' response, PFS, OS, and DOR

The density of CD8+ cells, CD3+ cells, and the expression of PD-1 and PD-L1 in the same cholangiocarcinoma tissue at baseline, after four weeks of combination olaparib and pembrolizumab therapy, at the time of cancer progression, and the changes between different time points will be summarized using descriptive statistics (N, Range, Median, Mean, STD). The paired t-test will be used to examine the changes in each biomarker level from the same tumor prior to any treatment at four weeks after the combination of olaparib and pembrolizumab, and at the time of cancer progression. These biomarkers levels and changes may be categorized into high or low levels based on the distribution of the data collected. The response of different biomarker levels (high vs. low) at baseline, at 4 weeks after combination treatment with olaparib and pembrolizumab, or at the time of cancer progression will be compared via Chi-Square test or Fisher's Exact test when appropriate. The relationship between these biomarker levels, their changes, and the DOR and PFS will be explored via Kaplan-Meier methodology and Log-rank test.

Similar analyses will be done for the Shannon Diversity Index (SDI) of T cell clonality in tumor samples.

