The expression of ERCC (DRCC+/-), and the mutation status of IDH1 or 2 (mutant or non-mutant) in the same cholangiocarcinoma tissue at baseline will be summarized using descriptive statistics (N, frequency). The response of ERCC- or IDH1/2 wild type tumors at baseline will be compared with the response of ERCC+ or IDH1/2 mutant tumor using Chi-Square test or Fisher's exact test when appropriate. The relationship between these biomarker levels and the DOR and PFS will be explored via Kaplan-Meier methodology and Log-rank test.

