Appendix 4: Description of the iRECIST Process for Assessment of Disease Progression

Assessment at Screening and Prior to RECIST 1.1 Progression

Until radiographic progression based on RECIST 1.1, there is no distinct iRECIST assessment.

Assessment and Decision at RECIST 1.1 Progression

In participants who show evidence of radiological PD by RECIST 1.1 the Investigator will decide whether to continue a participant on study treatment until repeat imaging is obtained (using iRECIST for participant management (see Table 5 and Figures 1 and 3). This decision by the Investigator should be based on the participant's overall clinical condition.

Clinical stability is defined as the following:

- Absence of symptoms and signs indicating clinically significant progression of disease
- No decline in ECOG performance status
- No requirements for intensified management, including increased analgesia, radiation, or other palliative care

Any participant deemed clinically unstable should be discontinued from study treatment at site-assessed first radiologic evidence of PD, and is not required to have repeat tumor imaging for confirmation of PD by iRECIST.

If the Investigator decides to continue treatment, the participant may continue to receive study treatment and the tumor assessment should be repeated 4 to 8 weeks later to confirm PD by iRECIST, per Investigator assessment. I

Tumor flare may manifest as any factor causing radiographic progression per RECIST 1.1, including:

- Increase in the sum of diameters of target lesion(s) identified at baseline to $\geq 20\%$ and ≥ 5 mm from nadir
 - Please note: the iRECIST publication uses the terminology “sum of measurements”, but “sum of diameters” will be used in this protocol, consistent with the original RECIST 1.1 terminology.
- Unequivocal progression of non-target lesion(s) identified at baseline
- Development of new lesion(s)

iRECIST defines new response categories, including iUPD (unconfirmed progressive disease) and iCPD (confirmed progressive disease). For purposes of iRECIST assessment, the first visit showing progression according to RECIST 1.1 will be assigned a visit (overall) response of iUPD, regardless of which factors caused the progression.

A Phase II, Single-arm Study of Combination Pembrolizumab and Olaparib in the Treatment of Patients with Advanced Cholangiocarcinoma

Version 2.1: 17Mar2023

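### Section 8.2.3 uses response only as yes/no in the biomarker analyses, formally tests DOR in about 6 to 12 responders, and gives no method for OS, which the objectives name

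*Combined protocol and SAP*

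**What the plan says.** Section 3.3, objectives 1, 2 and 4, plans to correlate biomarkers with four outcomes; objective 4, for example, relates "the baseline mutation status of IDH1 or 2 (mutant or non-mutant) with ORR, DOR, PFS, and OS". Section 8.1.1.2 lists the same four outcomes, and the SAP text in 8.2.3 repeats the intention: "we are interested in correlating them with patients' response, PFS, OS, and DOR".

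The methods in 8.2.3 are narrower.

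- **Response, tissue markers** (high versus low): "will be compared via Chi-Square test or Fisher's Exact test when appropriate".
- **Response, ERCC and IDH1/2:** "compared with the response of ERCC+ or IDH1/2 mutant tumor using Chi-Square test or Fisher's exact test when appropriate".
- **Time to event, tissue markers:** "The relationship between these biomarker levels, their changes, and the DOR and PFS will be explored via Kaplan-Meier methodology and Log-rank test".
- **Time to event, ERCC and IDH1/2:** "The relationship between these biomarker levels and the DOR and PFS will be explored via Kaplan-Meier methodology and Log-rank test".

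Neither log-rank sentence includes OS, and T-cell clonality is to be analysed in the same way, so it inherits the gap. Section 3.2 measures DOR from best overall response to progression. PFS runs from registration in all patients (4.5.2, 8.1.1.2). Tumour size is available: 5.2 requires measurable disease, 7.1.2.6.2 schedules repeat scans from week 6, and Appendix 4 works with the target-lesion sum, as in "Increase in the sum of diameters of target lesion(s) identified at baseline". No analysis uses that sum as a continuous outcome.

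**The concern.** Three things do not fit together.

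- An outcome promised in both lists of objectives and in the SAP's own statement of interest has no method. In an open-label trial, any OS-by-biomarker analysis would then be chosen with the data in view.
- The one outcome defined only for responders gets a formal test. Besides being small, that comparison conditions on something that happens after treatment starts, so it does not compare the marker groups as enrolled.
- Tumour change is reduced to a yes/no split in about 33 patients, which discards information that the scans already hold.

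At stake is how much the trial can learn about ERCC1 and IDH1/2, its stated biological rationale (3.3, 4.4.1.1), for which patients are asked to have up to three biopsies (2.1). The ORR decision is not at stake.

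**Working it through.** **Starting point.** The plan gives no power for any biomarker analysis, so there is no such figure to reproduce. The response rates and sample size come from 8.1.1.3. Its two-stage rule (stop at 2 or fewer of 13; do not reject at 8 or fewer of 33), summed exactly over the binomial, gives type I error 0.0922 at 17.5% and power 0.8084 at 35%, so type II error 0.1916. These match the printed 0.092 and 0.192, so 17.5%, 35% and n=33 are used below.

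**Number with a DOR.** 33 × 0.175 = 5.8 and 33 × 0.35 = 11.6, so about 6 to 12 patients.

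**Expected events for OS and PFS.** Inputs: medians of 40 weeks (OS) and 24 weeks (PFS) from 3.2; accrual A = 21 months (5.1) or 24 (1.0, taken as months); total T = 36 months. Assume exponential survival and uniform accrual, with λ = ln 2 / median:

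P(event) = 1 − [exp(−λ(T−A)) − exp(−λT)] / (λA)

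For 33 patients this gives 27.6 or 26.8 deaths and 31.2 or 30.7 PFS events. I use 26 deaths (slightly cautious) and 31 PFS events.

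**Log-rank power at an assumed hazard ratio of 2, two-sided 0.05.** Power = Φ(√(d·q(1−q))·ln 2 − 1.96), with d events and share q in one group.

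| Outcome | Events | Equal groups | 25/75 split |
|---|---|---|---|
| DOR | 6 | 13% | 11% |
| DOR | 12 (every responder progresses) | 22% | 18% |
| OS | 26 | 42% | 33% |
| PFS (already planned) | 31 | 49% | 39% |

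Example, OS with equal groups: √(26/4) × 0.693 − 1.96 = −0.19, and Φ(−0.19) = 0.42. OS is far more informative than DOR, but not more than PFS.

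**Response as yes/no versus tumour change.** Group sizes: IDH mutant 25% of 33, about 8; low ERCC1 74% of 33, about 24 (both shares from 4.4.1.1); and an even split. Assumed response rates keep the overall rate near 35%: (8×0.60 + 25×0.27)/33 = 0.350; (24×0.43 + 9×0.13)/33 = 0.348; (16×0.50 + 17×0.20)/33 = 0.345.

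Model, all assumed: best percent change is normal with SD 35, floored at −100%; response means a change of −30% or lower; group means are set to give the stated rates. The shift in SD units is then z(p1) − z(p2), for example 0.253 − (−0.613) = 0.87 for 60% v 27%. It does not depend on the SD or the cut. What matters is normality and a pure shift.

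In the second pair of columns, 10% have no post-baseline scan (worst rank, non-responder) and 10% have new lesions (non-responder, measured change kept).

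| Groups (response rates) | Fisher, complete | Wilcoxon, complete | Fisher, 10% + 10% | Wilcoxon, 10% + 10% |
|---|---|---|---|---|
| IDH 8 v 25 (60% v 27%) | 38% | 52% | 28% | 35% |
| ERCC 24 v 9 (43% v 13%) | 29% | 63% | 21% | 44% |
| Even 16 v 17 (50% v 20%) | 39% | 60% | 29% | 44% |

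A repeat run of the model agreed to within about 4 points. A check without simulation, for the IDH case with complete data, gives 37% by exact enumeration of Fisher's test and 54% by noncentral t on the latent scale. Null rejection is about 3% for Fisher and about 5% for Wilcoxon, so part of the gain reflects Fisher's conservatism.

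**Sensitivity.** If patients with new lesions are also ranked worst, little or no gain remains in two of the three scenarios. A related variant, with 10% unassessed and shrinkers not counted as responders also ranked worst, gives Wilcoxon 34-40% against Fisher 29-37%.

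**The case against.** The strongest reply is that the plan already has an all-patient time-to-event test. PFS counts death, covers everyone registered and is compared by log-rank in both method sentences. A reader might infer from the gaps that the plan wastes its survival data or looks only at responders. The documents do not support that. OS is also named in 8.2.3; what is missing is its method. With about 31 PFS events against 26 to 28 deaths, adding OS gains no power. All of this stands.

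Second, the tumour-size gain depends on the model. SD 35, normality and a pure shift have no source in the documents. The SAP also allows chi-square: for 16 v 17, exact enumeration gives 46% (null size 5.7%), which narrows the gap with Wilcoxon's 60% from 21 to 14 points. The two unequal splits remain Fisher cases. This stands as a limit on the size of the gain.

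Third, a reader might infer that target-lesion change should replace RECIST response as the lead outcome. The documents do not support that either. Section 7.1.2.6.5 makes RECIST 1.1 the primary measure, and Appendix 4 lists new lesions among the causes of RECIST 1.1 progression, so a patient who is progressing through new lesions could rank well on target lesions. The measure also appears in no list of objectives or endpoints. It belongs beside the response table, not above it.

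Fourth, the analyses are exploratory, unpowered and tied to no decision rule, and nothing says that a null result would count against the hypothesis. That holds, and it keeps this a modest point. It does not supply the missing OS method or justify a formal test on DOR.

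**Conclusion.** The point holds as a cheap improvement to 8.2.3. Three facts rest on the text alone: response enters only as yes/no, OS is promised three times without a method, and DOR gets a log-rank test although only responders have it.

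The sizes rest on assumptions. At a hazard ratio of 2, the DOR test has about 11-22% power with 6 to 12 events. Adding tumour change lifts power from about 29-39% to 52-63% with complete data, and from 21-29% to 35-44% with 10% unassessed and 10% new lesions. This requires a normal shift of about 0.84 to 0.95 SD and all 33 patients having marker data. Biopsies may be waived (5.2 and the flow chart footnotes), so the real numbers may be smaller. Most of the gain goes if patients with new lesions are ranked worst. Even with the change, a true effect of this size could easily be missed.

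**What to change.** Amend 8.2.3 in three places.

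1. Keep the chi-square or Fisher comparison of RECIST response. Alongside it, prespecify best percent change from baseline in the sum of target-lesion diameters: a Wilcoxon test for ERCC1 and IDH1/2, and rank correlation for continuous markers. Keep the measured value for assessed patients and give worst rank to those with no post-baseline scan. Add a sensitivity analysis that also ranks patients with new lesions worst.
2. Add OS to both Kaplan-Meier and log-rank sentences, and keep PFS in both.
3. Report DOR by biomarker descriptively (number of responders, individual durations, Kaplan-Meier curve), without a formal test.

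The cost is SAP wording and a few lines of analysis code. No new scans or visits are needed, provided that the case report form records the target-lesion sums, which should be confirmed. The downsides are a few more exploratory tests, and a size measure that ignores new and non-target lesions, which is why RECIST response stays in the analysis.

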4.0 BACKGROUND & RATIONALE

4.1 Cholangiocarcinoma

Cholangiocarcinoma has been steadily increasing in incidence worldwide over the last decade [1]. It is difficult to establish the diagnosis of early stage cholangiocarcinoma as symptoms are not prominent until the disease is far advanced. Patients with unresectable tumors have a dismal prognosis, with a median survival time of nine months [2,3]. Surgical resection is considered to be the most viable approach to attempting a “cure” for cholangiocarcinoma but even after surgery, five-year survival rates range from only 25% to 48% due to incomplete resection and a subsequent high recurrence rate (~50%) [4-6]. New approaches are urgently needed to prevent tumor recurrence after surgical resection in an attempt to further improve patient survival.

4.1.1 Chemotherapy and Cholangiocarcinoma

A recent randomized, controlled trial (ABC-02 study) proved that gemcitabine combined with cisplatin (GC-therapy) performed better than gemcitabine monotherapy for cholangiocarcinoma [7]. However the benefits of GC-therapy were shown to be modest with a progression free survival (PFS) of 8.1 months and overall survival (OS) of 11.7 months [7]. Furthermore there is no effective

A Phase II, Single-arm Study of Combination Pembrolizumab and Olaparib in the Treatment of Patients with Advanced Cholangiocarcinoma

Version 2.1: 17Mar2023

second line therapy for patients with advanced cholangiocarcinoma. In a Phase II study of second line gemcitabine monotherapy for cholangiocarcinoma in patients refractory to 5-fluorouracil treatment, the median time to progression (TTP) was 1.6 months (95% CI: 1.3-1.9 months), and the median OS was 4.1 months (95% CI: 2.7-5.5 months) [8]. A retrospective analysis of patients with metastatic gallbladder cancer and cholangiocarcinoma who were treated with second-line FOLFOX4 chemotherapy after disease progression on gemcitabine-based first-line chemotherapy demonstrated stable disease in 22% of patients, a median disease free survival (DFS) of 96 days (13 weeks), and an OS of 138 days (19 weeks)[9].

